Compression Wraps as adjuvant therapy in the management of acute systolic heart failure (CATAS-HF trial)

8/1/2020

- Study Protocol &
Statistical Analysis Plan

NCT# NCT04095416

STUDY TITLE: Compression wraps as adjuvant therapy in the management of acute systolic heart failure (CATAS-HF)**• STUDY AIM, BACKGROUND, AND DESIGN ABSTRACT**

Our goal is to measure the application of lower extremity compression wrapping as adjuvant therapy to diuresis in the management of patients hospitalized for acute systolic heart failure. Use of compression wrapping will be assessed through randomized parallel intervention clinical trial of patients admitted to Henry Ford Hospital I5 Cardiology service for management of acute systolic heart failure presenting with lower extremity edema. Enrolled patients will be managed with standard medical therapy, with (intervention) or without (control) the adjuvant use of lower extremity compression wrapping. Efficacy of the intervention will be analyzed for the following primary endpoints: 1) Percentage difference in weight before and after diuresis 2) Percent difference in Brain natriuretic peptide (BNP) from admission to discharge; 3) Difference in length of admission in days. Our hypothesis is adjuvant use of lower extremity compression wraps to standard medical therapy increases percentage of weight reduction achieved with diuresis, increases percent reduction in BNP after diuresis, and decreases total length of stay for patients hospitalized with acute systolic heart failure.

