Patients will be enrolled exclusively based on inclusion and exclusion criteria, undergoing randomization into intervention or control groups. No screening tools will be used.

• STUDY PROCEDURES

The study will be an internally funded, parallel-intervention clinical trial studying the use of lower extremity compression stockings as adjuvant therapy to standard medical care in management of patients admitted for acute systolic heart failure. There will be two arms, intervention and control. 120 patients will be enrolled in the study, 60 to each arm, to achieve power above 80% with an alpha of 0.05, measuring continuous primary endpoints of average percent reduction in weight after diuresis, average change in BNP from admission to discharge, and average length of admission in days.

Data will be collected by Henry Ford personnel, for 120 patients previously admitted after January 2018 and managed on the HF Main cardiology I5 floor meeting inclusion criteria and managed with standard medical therapy without the use of compression stockings, and will undergo review by research team for enrollment into the control group. If additional patients are needed to achieve enrollment number of 60 control subjects, patients will be enrolled and randomized prospectively by the research team. Data collected retrospectively will be performed through Epic health medical record and charted on Excel spreadsheet, and will include admission length of stay, daily weights, daily urine outputs, daily diuretic dose and type(s) used, admission BNP, and discharge BNP. Research team will also perform chart review on enrolled patients to evaluate for 30-day readmission rate.

The intervention arm will include patients enrolled and randomized by the research team meeting inclusion criteria, and managed on HF Main cardiology I5 floor. This population will receive bilateral lower extremity compression wraps (ACE bandages) on day 1 of admission in addition to standard medical therapy. Data will be collected by the research team through Epic health medical record and will be charted on Excel spreadsheet, and will include admission length of stay, daily weights, daily urine outputs, daily diuretic dose and type(s) used, admission BNP, and discharge BNP. These charts will also undergo review by research team to evaluate for 30-day readmission rate.

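### The trial is called randomised, but its 60 control places are filled first from past charts, so it may contain no randomised comparison, and no adjustment is specified

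*Combined protocol and SAP*

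**What the plan says.** The design abstract states: "Use of compression wrapping will be assessed through randomized parallel intervention clinical trial". The end of Subject Population and Eligibility repeats this for everyone enrolled: "Patients will be enrolled exclusively based on inclusion and exclusion criteria, undergoing randomization into intervention or control groups".

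Study Procedures describes the two arms differently.

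- **Intervention arm.** Prospective, and called randomised without condition: "The intervention arm will include patients enrolled and randomized by the research team meeting inclusion criteria".
- **Control arm, first source.** Data are collected "for 120 patients previously admitted after January 2018 and managed on the HF Main cardiology I5 floor meeting inclusion criteria", treated without compression, and these patients "will undergo review by research team for enrollment into the control group".
- **Control arm, second source.** Used only if the first falls short: "If additional patients are needed to achieve enrollment number of 60 control subjects, patients will be enrolled and randomized prospectively by the research team".

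The next paragraphs of Study Procedures confirm that control data are reviewed both retrospectively and prospectively. The planned analysis consists of descriptive summaries, univariate group comparisons, t-tests, and ANOVA with post-hoc tests. No covariate, matching, weighting, calendar-period term or separate analysis of randomised patients is mentioned.

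**The concern.** These statements cannot all hold. A 1:1 randomisation that yields 60 intervention patients also yields about 60 concurrent controls, and then charts are not needed. If charts supply the controls, being randomised means nothing for the intervention arm, because there is no other arm to which those patients could have been allocated.

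Three consequences follow.

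- **Label.** The study could be reported as a randomised trial with no randomised comparison in it.
- **Period and selection.** Historical controls can differ from the intervention patients in calendar period and in how they were chosen. No rule says which charts are used if more than 60 qualify, and the outcomes sit in the same record the team works from: "Data collected retrospectively will be performed through Epic health medical record and charted on Excel spreadsheet, and will include admission length of stay", followed by weights and BNP. The eligibility section also treats wrapping as existing practice, so past patients who were not wrapped may differ from those who would have been.
- **Analysis.** With unadjusted tests, any such difference enters all three primary endpoints. It can create an apparent benefit or hide a real one.

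Consent and capacity requirements for prospective patients are a possible further difference from charted controls, but not an established one.

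**Working it through.** **1. Can the control arm be wholly historical?** Inputs from Study Procedures: 120 candidate charts, 60 control places. With an assumed acceptance proportion *y*, the randomised top-up is max(0, 60 − 120*y*).

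| Accepted charts | Randomised controls |
|---|---|
| 50% or more (60 to 120) | 0 |
| 40% (48) | 12 |
| 30% (36) | 24 |

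The 120 are described as already meeting the inclusion criteria, so a top-up of zero is realistic.

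**2. The plan's own figure.** Study Procedures claims power above 80% with 60 per arm at alpha 0.05. It gives no effect size or SD, so the claim cannot be reproduced. Solving back, with a two-sided test assumed: (1.960 + 0.842) × √(2/60) = 0.51 SD. The noncentral t gives 0.516 SD, which is the reference effect below.

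**3. False-positive rate with no adjustment.** Assumptions: normal outcomes, 60 per arm, no wrap effect, historical controls shifted by *b* SD. None of the shifts comes from the documents. With all controls historical, the rejection rate is P(|T| > t₀.₉₇₅,₁₁₈), where T is noncentral t on 118 df with noncentrality *b*/√(1/60 + 1/60) = 5.48*b*. The mixed arms were simulated (200,000 runs each).

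| Historical controls | *b* = 0.1 | 0.2 | 0.3 |
|---|---|---|---|
| 60 of 60 | 8.4% | 19.2% | 37.1% |
| 45 of 60 | 6.9% | 12.7% | 22.8% |
| 30 of 60 | 5.8% | 8.2% | 12.7% |
| 15 of 60 | 5.2% | 5.8% | 6.8% |

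**4. A real benefit hidden.** If the true effect is 0.516 SD and all controls are historical, a shift against the wraps leaves 0.416, 0.316 or 0.216 SD. Power falls from 80% to 61.7%, 40.3% or 21.6%.

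**5. Chart selection.** As an upper bound, suppose the 60 charts taken are the extreme ones on a variable correlated *r* with the outcome. The control mean then shifts by *r* times the mean of the top 60 of *N* standard normals.

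| Qualifying charts *N* | Shift | Rejection at *r* = 0.25 |
|---|---|---|
| 120 | 0.79*r* | 19.0% |
| 90 | 0.54*r* | 11.3% |
| 60 | 0 | 5.0% |

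Looser selection does less. Drawing 60 of 120 charts with weights exp(0.5*z*) shifts the mean by 0.32*r*, which is 0.08 SD at *r* = 0.25 and gives about 7% rejection.

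**6. What a randomised top-up could rescue.** Effect detectable with 80% power in a concurrently randomised subset:

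| Intervention / control | Detectable effect |
|---|---|
| 60 / 60 (planned size) | 0.52 SD |
| 60 / 30 | 0.63 SD |
| 30 / 30 | 0.74 SD |
| 60 / 10 | 0.97 SD |
| 10 / 10 | 1.33 SD |

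The rows with 60 intervention patients assume that all of them are concurrent with the top-up controls.

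**The case against.** The strongest reply is that the text is contradictory rather than plainly non-randomised. Under the eligibility section's sentence concurrent controls would exist, so the absence of a randomised comparison is only one possible outcome. That is right, and the point is put conditionally. But nothing in the document says which statement governs, and the only operational description of how controls are obtained is the chart-first one.

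The analysis paragraph says what the analysis will include, which need not be exhaustive. ANOVA with post-hoc tests might even imply three groups, with historical and randomised controls kept apart. This stands to the extent that the fair wording is that no adjustment or separation is specified. The three-group reading is hard to sustain, since Study Procedures states "There will be two arms, intervention and control" and the tests are described by treatment group.

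Enrolment is said to rest on the eligibility criteria alone, and nothing suggests that charts would be picked for their outcomes. That is also fair, and the selection figures are a bound, not a prediction. Eligibility criteria still do not choose among surplus eligible charts, nor do they balance the arms.

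Finally, all the shifts are assumed, and a normal model is doubtful for length of stay. This limits the figures to illustration. The design defect does not depend on them.

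**Conclusion.** The concern holds. The allocation statements conflict. Under the only procedure the plan describes for obtaining controls, acceptance of 60 of the 120 charts leaves no randomised comparison. With fewer, the randomised part is smaller than planned and its size is not fixed in advance. No adjustment or separate analysis is specified.

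The size of any bias cannot be derived from the documents. With all controls historical, an assumed shift of 0.2 SD takes a 5% test to about 19%, or cuts 80% power to about 40%. The effect shrinks as the historical share falls. These figures assume normal outcomes and a two-sided t-test.

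This must be fixed. It affects all three primary endpoints and decides whether the study may be called randomised. It cannot be fully repaired later: charts chosen with outcomes in view cannot be unchosen, and concurrent controls cannot be recruited after the fact.

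**What to change.** Reconcile the design abstract, the eligibility section and Study Procedures on allocation. If charts remain the main source of controls:

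- Describe the study as a prospective intervention cohort with historical controls. Keep the word randomised for any subset in which both arms were randomised concurrently.
- Take charts by a fixed, outcome-blind rule, such as consecutive eligible admissions until 60 are reached.
- Prespecify an adjusted model for each primary endpoint. Admission weight and admission BNP are natural covariates and already collected; age and ejection fraction are eligibility items to add to the data form. Neither of the first two is a baseline for length of stay, so adjustment is weakest there.
- Report randomised top-up controls separately, and compare them only with intervention patients randomised over the same period.
- Limit the main conclusion to association, and state that adjustment cannot remove a period effect.

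The cost is protocol and SAP wording, matching changes to the study description in the consent document with the review that such changes need, two data items, a chart rule and three regression models. The claim becomes more modest.

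Randomising all 120 patients concurrently, with charts as supportive data only, would be stronger and keeps the total at 120. It is not cheap: up to 60 more patients must be recruited prospectively. Time is short on the plan's own dates. The document is dated 8/1/2020, Study Procedures gives tentative completion as January 2021, and the consent section gives January 2020. Those two completion dates also need reconciling.

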Lower extremity compression wraps are a low cost inpatient intervention when managing fluid overload in patients hospitalized for acute systolic heart failure, and presenting with lower extremity edema. Also, compression stockings are mainstay devices in the outpatient setting for improving symptoms of lower extremity edema in chronic systolic heart failure. However, the utility of compression wraps in managing patients hospitalized for acute systolic heart failure, and transitioning to the use of compression stockings for symptom management upon discharge, has not been thoroughly assessed. Current practice suggests use of lower extremity compression wraps can facilitate intravenous diuresis while inpatient, achieve more optimal discharge dry weight, and lower BNP levels prior to discharge. Demonstrating efficacy of such a low-cost, low-risk intervention in decreasing hospital stay and achieving more favorable patient outcomes will have considerable impact on standard practice.

• SUBJECT POPULATION AND ELIGIBILITY

Inclusion criteria: patients age greater than 18 and less than 85 years of age, admitted to I5 with Acute Systolic Heart Failure, and an ejection fraction of less than 50% as determined by echocardiogram within 6 months, requiring inpatient management with intravenous diuretic therapy. Must have a diagnosis of acute systolic heart failure (by ICD coding) on admission, of any underlying etiology. Must have documentation of pitting edema on primary assessment.

Exclusion criteria: patients who do not meet inclusion criteria, who cannot tolerate IV diuresis, who cannot wear or tolerate lower extremity compression stockings or wraps; active diagnosis of ESRD on dialysis or peripheral neuropathy; ejection fraction greater than 50% as evaluated by echocardiogram within 6 months.

Control population: Patients meeting inclusion criteria, managed on I5 for acute systolic heart failure with standard medical therapy without the use of lower extremity compression wraps.

This will allow direct comparison of the effect of intervention (lower extremity compression wraps) on the previously listed endpoints on the same patient population.

Since this study evaluates an already established component of standard medical practice, there will be no discrimination of patient populations in enrollment outside of the inclusion and exclusion criteria.

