Co-investigators will be responsible for retrospective and prospective data review for control population. Both co-investigators and sub-investigators will be responsible for enrolling patients in the study and collecting above mentioned data points. Nursing staff on the floor will undergo teaching on application of ACE compression wraps, and will be responsible for capturing physician order for wrap application and executing order, which will mark the beginning of the trial enrollment.

Data analysis will be conducted through the Division of Biostatistics and Research Epidemiology and will include descriptive statistics and univariate comparisons between treatment groups. T-test and ANOVA with post-hoc analysis will be used to evaluate for difference in the means of each endpoint previously listed for each treatment group. Patient information will be de-

identified prior to data analysis. Data for enrolled patients will be saved on secure Henry Ford Health System servers on Microsoft OneDrive cloud servers and shared among research team. Identifiers will include MRNs to access patient charts, collect and verify data, and perform review for 30-day readmission rates. Data will be stored for the entirety of the study, and promptly discarded in accordance with HFHS regulation at the completion of the study tentatively scheduled for January 2021. Data collected on patients excluded from the study will be discarded at the time of exclusion in accordance with HFHS regulation. Missing or incomplete data will prompt withdrawal of particular patient from study, and will factor into final data analysis as an intention to treat value.

Total time of subject enrollment in the study: duration of hospital stay. No additional visits or follow-up testing is required.

Literacy and language barrier concerns will be handled on a case-by-case basis, primarily using standard communication methods of translator services.

- **ANTICIPATED RISKS**

There are no significant anticipated risk beyond standard of care risk in management of patients with acute systolic heart failure. Intervention includes an already established therapy on patients with lower extremity edema. We are simply testing the formal efficacy of this intervention in an interventional study.

- **ANTICIPATED BENEFITS**

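### The data list omits most baseline prognostic factors and the analysis is unadjusted, although controls come first from past, non-randomized admissions

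*Combined protocol and SAP*

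**What the plan says.** All references are to the combined protocol and SAP.

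- **Data collected (Study Procedures).** The same list appears for the retrospective data and for the intervention arm. The data "will include admission length of stay, daily weights, daily urine outputs, daily diuretic dose and type(s) used, admission BNP, and discharge BNP". One outcome is added: "Research team will also perform chart review on enrolled patients to evaluate for 30-day readmission rate".
- **Source of controls (Study Procedures).** Data are gathered "for 120 patients previously admitted after January 2018 and managed on the HF Main cardiology I5 floor meeting inclusion criteria", and the research team reviews these patients for entry to the control group. Randomized controls are a top-up: "If additional patients are needed to achieve enrollment number of 60 control subjects, patients will be enrolled and randomized prospectively by the research team".
- **Size (Study Procedures).** "120 patients will be enrolled in the study, 60 to each arm, to achieve power above 80% with an alpha of 0.05". No effect size or SD is given for any endpoint.
- **Analysis (Study Procedures).** The plan is for "descriptive statistics and univariate comparisons between treatment groups", with t-tests and ANOVA on the endpoint means. No covariate is named.
- **Eligibility (Subject Population and Eligibility).** Age, ejection fraction, presence of pitting edema and dialysis status decide entry. Nothing says whether these values are recorded for enrolled patients.
- **Access and retention (Study Procedures).** Medical record numbers are kept so that charts can be opened and data collected and verified. Study data are to be "promptly discarded in accordance with HFHS regulation at the completion of the study tentatively scheduled for January 2021".

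**The concern.** Randomization does not protect the main comparison if the control arm is filled from past charts, and the plan itself lets the arms differ in three ways:

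- **Calendar time.** Past controls are compared with prospectively enrolled wrap patients.
- **Consent.** The Consent section lets prospective patients refuse and bars those with diminished capacity or any impairment. No matching filter is described for past charts.
- **Selection.** Data from 120 past patients are reviewed for 60 control places, with no selection rule stated.

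The population section nevertheless presents the two groups as the same patient population. The listed fields can test that only through admission BNP, first weight and first-day diuretic dose. Admission weight does not separate fluid from body mass, so it is a poor stand-in for edema severity when the endpoint is percent weight loss. A difference in congestion or illness severity could bias any of the three primary endpoints, and an unadjusted test would read it as a wrap effect or as its absence.

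**Working it through.** **Step 1: check the list.**

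| Item | On the data list? | Mentioned elsewhere? |
|---|---|---|
| Admission BNP, first weight | Yes | BNP and weight endpoints |
| First-day diuretic dose | Yes, as treatment given | No |
| Age, ejection fraction | No | Eligibility |
| Edema grade | No | Only presence of pitting edema, for eligibility |
| Kidney function | No | Only dialysis status, for eligibility |
| Home diuretic | No | No |
| Admission date | No | Defines past controls (after January 2018) and is needed to compute length of stay |

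**Step 2: the plan's own figure.** Power above 80% cannot be reproduced without an effect size and SD. Taking a two-sided test (sidedness is not stated), the standardised difference detectable with 80% power at 60 per arm is, by normal approximation,

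(1.960 + 0.842) × √(2/60) = 0.51 SD.

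The one-sided value is 0.45 SD. The stated power can therefore be neither confirmed nor refuted, but 0.51 SD gives a scale for judging bias.

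**Step 3: effect of an unrecorded factor.** Suppose a baseline factor differs between arms by D SD and has correlation r with the endpoint. The unadjusted difference is then biased by about r × D SD. With no true wrap effect, the t statistic is noncentral t with 118 degrees of freedom and noncentrality (bias) × √(60/2). D and r are assumptions; the documents give neither.

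| Assumed D, r | Bias (SD) | Share of 0.51 SD | Two-sided 5% test rejects |
|---|---|---|---|
| 0.2, 0.2 | 0.04 | 8% | 5.5% |
| 0.2, 0.3 | 0.06 | 12% | 6.2% |
| 0.5, 0.2 | 0.10 | 20% | 8.4% |
| 0.5, 0.3 | 0.15 | 29% | 12.9% |
| 0.4, 0.5 | 0.20 | 39% | 19.2% |
| 0.5, 0.5 | 0.25 | 49% | 27.4% |
| 0.6, 0.5 | 0.30 | 59% | 37.1% |
| 0.8, 0.5 | 0.40 | 78% | 58.4% |

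Bias of 0.1 to 0.3 SD thus turns a nominal 5% error rate into about 8% to 37%. Mild imbalance does little harm. With the listed fields, nobody could tell which row applies.

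**Step 4: room for adjustment.** The fix below proposes eight covariates plus admission weight and admission BNP. If each enters as a single term, these ten with arm and an intercept make 12 coefficients, leaving 120 − 12 = 108 residual degrees of freedom.

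**The case against.** A reader might infer that baseline differences can never be shown or corrected. The documents do not support that. Admission BNP and first weight are recorded and could be compared and adjusted for now. Record numbers allow further abstraction while the study is open. What is discarded at completion is study data; nothing says the hospital chart is destroyed.

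A reader might also infer that eligibility values are looked up and then thrown away. The plan discards data at exclusion for excluded patients and is silent on eligibility values for enrolled ones. Its list is not declared exhaustive, and descriptive statistics are planned. The accurate statement is that these fields are not specified.

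A third tempting inference is that wraps were already routine on this floor, so unwrapped past patients had different edema. The population section says only "Since this study evaluates an already established component of standard medical practice". It gives no wrap rate for the floor, and the Alternatives section says the intervention is not an established efficacious therapy. A difference in edema severity is possible but not documented.

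The error rates rest on assumed D and r, and they ignore whatever part of an imbalance admission BNP and weight already capture. The deeper problem is the use of past controls in a trial called randomized: any concurrently randomized controls would not share this problem, and extra fields cannot fully repair historical ones.

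These points narrow the concern but do not answer it. Followed as written, the plan still produces an unadjusted and largely non-randomized estimate with little means of checking it.

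**Conclusion.** The concern holds in limited form. Most baseline prognostic factors are not specified for collection, and no adjustment is planned, even for the baseline measures that are recorded. Imbalance between past controls and wrap patients can be assessed only through admission BNP, first weight and first-day diuretic dose.

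The size is illustrative: about 8% to 37% false rejections for an assumed bias of 0.1 to 0.3 SD, and 5% to 6% for milder imbalance. This takes a two-sided test, 60 per arm, no true effect, and a control arm made up mainly of past admissions. It is not a finding that the arms do differ, and the direction of any bias is unknown. Correcting the plan is a cheap improvement.

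**What to change.** While charts are accessible and before study data are discarded:

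1. Add to the Study Procedures data list, for both arms: age, sex, ejection fraction, edema grade where documented, creatinine, systolic blood pressure, home diuretic dose, prior heart failure admission and admission date. Abstract these before outcomes.
2. Report standardised differences by arm for every baseline field.
3. For all three primary endpoints (weight, BNP and length of stay), make the main estimate a model adjusted for, or weighted on, these fields other than admission date, plus admission weight and admission BNP. Show the unadjusted result beside it.
4. Use admission date only to describe calendar drift, for example the outcome trend within past controls. It nearly determines arm, so as a covariate it would make the effect depend on extrapolation, and as a propensity term it would leave no overlap.
5. State that a missing covariate does not trigger the rule that withdraws patients with missing or incomplete data, and name a missing-covariate method instead.
6. State that adjustment reduces but does not remove the bias from non-concurrent controls.

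The cost is nine fields from charts already under review, a short analysis paragraph and some abstraction time. Some covariates will be missing, notably edema grade in past charts, because eligibility requires only that pitting edema be documented.

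### The team that enrols also randomises, no concealment or consecutive-approach rule is described, and charts fill the control arm first, so a wrap assignment can be known or anticipated when choosing whom to approach

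*Combined protocol and SAP*

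**What the plan says.** All references are to the combined protocol and SAP.

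- **Size (STUDY PROCEDURES).** "120 patients will be enrolled in the study, 60 to each arm, to achieve power above 80% with an alpha of 0.05".
- **Controls (STUDY PROCEDURES).** Data are collected "for 120 patients previously admitted after January 2018 and managed on the HF Main cardiology I5 floor meeting inclusion criteria", and these patients "will undergo review by research team for enrollment into the control group". Prospective controls are a top-up: "If additional patients are needed to achieve enrollment number of 60 control subjects, patients will be enrolled and randomized prospectively by the research team".
- **Wrap arm (STUDY PROCEDURES).** "The intervention arm will include patients enrolled and randomized by the research team meeting inclusion criteria".
- **Roles.** STUDY PROCEDURES gives review of the control data to the co-investigators and adds: "Both co-investigators and sub-investigators will be responsible for enrolling patients in the study and collecting above mentioned data points". CONSENT PROCESS AND DOCUMENTATION has the enrolling co-investigators and sub-investigators obtain consent.
- **Start of enrolment (STUDY PROCEDURES).** It is marked by the physician's order for wraps and its execution by nursing staff.
- **Selection (SUBJECT POPULATION AND ELIGIBILITY).** Enrolment is to rest only on the eligibility criteria, with no discrimination beyond them. "No screening tools will be used".
- **Analysis (STUDY PROCEDURES).** Univariate comparisons, with t-test and ANOVA.

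The document describes no sequence generation, prospective allocation ratio, block size, concealment method, separate holder of the list, rule for consecutive approach, or log of patients not approached.

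**The concern.** Randomisation protects a comparison only if the person deciding whether to approach a patient cannot foresee the arm. Here the team that recruits also assigns, and part of it knows how many control places the charts have filled. If the charts fill all 60, every prospective patient receives wraps and everyone recruiting can know it. If they fill some, wraps are the more likely assignment.

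The stated hypothesis favours wraps on all three primary endpoints. A recruiter who shares it may, without intending to, pass over patients who look likely to do badly. Chart controls went through no such choice. The wrap arm could then start with a better prognosis, and the planned comparison, which adjusts for no baseline factor, would count that as benefit.

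**Working it through.** **1. The plan's own figure.** No effect size or SD is given, so the power statement can only be inverted. With 60 per arm and 80% power, the standardised difference is (1.960 + 0.842) × √(2/60) = 0.511 two-sided, or (1.645 + 0.842) × √(2/60) = 0.454 one-sided. The plan does not state which. This gives a scale for the shifts below and has no other bearing on the point.

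**2. Share of prospective patients who get wraps.** Let c be the control places filled from charts and k = 60 − c. Wraps are 60 of the 60 + k prospective patients, which is also the hit rate of always guessing wraps.

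| c | k | 60/(60+k) |
|---|---|---|
| 0 | 60 | 60/120 = 50% |
| 30 | 30 | 60/90 = 67% |
| 40 | 20 | 60/80 = 75% |
| 50 | 10 | 60/70 = 86% |
| 60 | 0 | 60/60 = 100% |

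The text permits the whole range. The upper end is likely because 120 charts, described as already meeting the inclusion criteria, are reviewed for 60 places: accepting half of them gives k = 0.

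**3. What selective approach could do (assumed inputs).** Suppose recruiters pass over the share q of eligible patients they expect to do worst, and that expectation correlates ρ with the outcome. Neither value is in the documents; I take q = 0.1-0.3 and ρ = 0.3-0.5. The selected group's mean shifts by ρ·φ(z)/(1 − q) SD, with z the normal quantile at 1 − q. Example: q = 0.2, ρ = 0.5 gives 0.5 × 0.280/0.8 = 0.175 SD. Rejection under no treatment effect comes from the non-central t with 118 df and non-centrality shift × √30, at two-sided 5%, with the SD taken as unchanged.

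All controls from charts (k = 0):

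| q | ρ = 0.3: shift, rejection | ρ = 0.5: shift, rejection |
|---|---|---|
| 0.1 | 0.058 SD, 6.2% | 0.097 SD, 8.3% |
| 0.2 | 0.105 SD, 8.8% | 0.175 SD, 15.8% |
| 0.3 | 0.149 SD, 12.8% | 0.248 SD, 27.1% |

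With half the controls from charts (k = 30), a recruiter who always expects wraps selects the 30 prospective controls in the same way. Half the control arm shifts too, so the net difference halves to 0.03-0.12 SD and rejection falls to 5.3-10.4%.

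**4. Direction of the false positives.** In the lowest case with all chart controls (q = 0.1, ρ = 0.3), 82% of rejections favour wraps; in the other five cases at least 92% do. At k = 30 the lowest case gives 68%.

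**The case against.** **The percentages do not measure concealment.** 60/(60+k) is an allocation ratio, and a perfectly concealed list with the same places would give the same hit rate. Knowing the places left adds about one point: best guessing on a fixed list is right 67.7% of the time at k = 30, against 66.7%. This stands. The ratio shows how far wraps can be anticipated, and a concealed list at that ratio would not lower it.

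**The larger bias figures apply only at k = 0,** where no random assignment is left to conceal and the main defect is the historical control group. This also stands, and it is why both scenarios are shown. Who enters the wrap cohort is still discretionary at k = 0, and approach in admission order addresses that.

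**The plan says enrolment rests only on the eligibility criteria.** That counts against passing patients over on prognosis. It does not require every eligible patient to be approached, and it does not hide the next assignment. The sentence about screening tools does not settle whether a log is kept.

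**The plan is silent rather than explicit.** It does not say that no list is held elsewhere, and no randomiser is named beyond the research team. This stands as a limit on the wording. Followed as written, though, the procedure offers no protection.

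**Conclusion.** The point holds. As described, the prospective part of the trial has the research team enrolling and randomising, the enrolling investigators taking consent, and co-investigators also reviewing the charts that fill the control arm first. A wrap assignment can be known or anticipated at the moment of approach, and the univariate test cannot remove the resulting selection. Under the assumed q and ρ, the shift is 0.06-0.25 SD with 6-27% rejection if all controls are charts, and 0.03-0.12 SD with 5-10% if half are.

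A reader might infer more than the documents support:

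- **That predictability is at least 67%.** This needs at least 30 chart controls. The plan never states k, and the text permits 50-100%.
- **That the same individuals consent and randomise.** The text says only that the research team does the latter.
- **That every recruiter knows the control count.** This follows for co-investigators, who review control data and enrol. It is not stated for sub-investigators.
- **That all three primary endpoints are biased towards wraps.** The direction is most plausible for length of stay. Passing over the most fluid-overloaded patients could bias percent weight loss the other way.

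**What to change.** 1. **Assignment.** For any prospectively randomised patients, use a computer-generated list with randomly varying block sizes and a ratio fixed before the first prospective patient. The Division of Biostatistics and Research Epidemiology, already named for the analysis, should hold it and release each assignment only after eligibility and consent are logged.
2. **Approach.** Approach every eligible I5 admission in order of admission. Keep a de-identified log of those not approached or declining, with reasons, and report it. If k = 0, this is the main protection against selective entry.
3. **Chart window.** Close the chart-control window on a date before the first prospective enrolment. It now has a start (after January 2018) but no end, so a patient passed over for wraps could later become a chart control.

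The cost is a protocol amendment, a brief delay per assignment and minor log-keeping, with no extra patients or procedures. These steps do not cure the non-randomised historical controls, which need their own remedy.
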